11.0 CENTRAL REVIEW PROCEDURES AND TISSUE COLLECTION

11.1 Central Radiology Review

At the conclusion of the trial, a central review of x-rays and/or scans will be carried out if any responses have been claimed. For purposes of reporting, the results of both local and central radiology reviews will be included.

11.2 Central Pathology Review

There will be no central pathology review for this study.

## 12.0 STATISTICAL CONSIDERATIONS

### 12.1 Objectives and Design

The primary objective is to determine the intracranial objective response rate to concurrent dabrafenib and trametinib with stereotactic radiation in patients with BRAF mutation-positive malignant melanoma and brain metastases. There will be two cohorts based on the numbers of CNS metastases. Secondary endpoints include:

- Extra-cranial objective response rate and overall ORR.
- Duration of response.
- Intracranial and overall progression free survival.
- Overall survival.
- To evaluate the safety and tolerability of the regimen using the CTCAE v.4.

### 12.2 Primary Endpoints and Analysis

The primary endpoint is objective response rate in the brain. Based on the literature objective response rate is not influenced by the numbers of metastases that are treated by SRS [Follwell 2012]. However, toxicity may be different based on numbers of metastases treated. For this reason, patients will be evaluated for ORR; however, toxicity will be evaluated for two cohorts: those with 1-4 lesions and those with 5-10 lesions. Response will be assessed using RECIST v1.1. Results between cohorts will only be compared descriptively with one another and with previously published data. There will be an interim safety analysis for both radiation cohorts after 5 patients in each cohort have completed SRS with 4 weeks of follow-up time.

### 12.3 Sample Size and Duration of Study

We propose to target a 20% increase in intracranial ORR based on a baseline of 40% for SRS or dabrafenib alone [Follwell 2012; Liew 2011; Neal 2014; Sueng 1998] versus 60% ORR with the combination [Long 2016] difference with alpha and beta = 0.10. With a Simon two stage design there would be > 7 responses/18 patients in the first stage and 22/46 in the second stage. Assuming 10% inevaluable patients or dropouts, we propose a maximum of 50 patients.

We propose to evaluate secondary endpoints of safety and intracranial PFS in the two previously defined cohorts 1-4 and greater than 5-10 and to having at least 20-25 patients/cohort for these endpoints.

With accrual of 4-5 patients/month the accrual duration will take an estimated 12-18 months with an additional 6 months of follow-up to assess objective responses.

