## 8.0 CRITERIA FOR MEASUREMENT OF STUDY ENDPOINTS

### 8.1 Definitions

*Response Assessments:* The following algorithms will be used to support primary and secondary efficacy endpoints in the present trial.

*CNS Assessments:* For efficacy assessment in the CNS to support the primary endpoint of intracranial response, a protocol defined RECIST 1.1-based approach will be utilized with modifications that reflect the approach of the RANO-BM Working Group. RECIST 1.1, uni-dimensional longest diameter (LD) measurements will be used with a lower limit of size for defining a measurable lesion,  $> 1$  cm based on the baseline MRI of brain. CNS lesions  $< 1$  cm are non-target lesions. Best overall CNS response represents a composite of radiographic CNS target and non-target response (see definitions below), corticosteroid use, and clinical status.

*Extracranial Disease Assessments:* Assessment of response of extracranial disease will use RECIST 1.1.

*Overall Response Assessments:* Overall response assessment will be assessed using RECIST 1.1. Overall response will be measured as the sum of the LD of CNS + extracranial index lesions. The size cut-off of a measurable lesion in the extracranial compartment will follow the RECIST 1.1 definition of 1.0 cm.

- 8.1.1 Evaluable for adverse events. All patients will be evaluable for adverse event evaluation from the time of their first treatment.
- 8.1.2 Evaluable for response. All patients who have received at least one cycle of therapy and have their disease re-evaluated will be considered evaluable for response (exceptions will be those who exhibit objective disease progression prior to the end of cycle 1 who will also be considered evaluable). Patients on therapy for at least this period and who meet the other listed criteria will have their response classified according to the definitions set out below [Eisenhauer 2009].

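### At the plan's own 10% loss, the cap of 50 leaves 45 evaluable patients, one short of the 46 the Simon design needs, and a final cut-off is given only for 46

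*Combined protocol and SAP*

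**What the plan says.** Section 12.3 sets out to "target a 20% increase in intracranial ORR", from a "baseline of 40% for SRS or dabrafenib alone" "versus 60% ORR with the combination", "difference with alpha and beta = 0.10". The two-stage rule reads: "there would be > 7 responses/18 patients in the first stage and 22/46 in the second stage". The next sentence sets enrolment: "Assuming 10% inevaluable patients or dropouts, we propose a maximum of 50 patients".

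Section 8.1.2 defines who counts: "All patients who have received at least one cycle of therapy and have their disease re-evaluated will be considered evaluable for response". Patients who progress before the end of cycle 1 also count.

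The test pools the two cohorts. Section 12.2 says "Results between cohorts will only be compared descriptively with one another and with previously published data".

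Sections 8 and 12 give no final boundary for an evaluable number other than 46. They have no rule for replacing inevaluable patients and none for counting them as non-responders.

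**The concern.** There are two linked problems.

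1. The design size, the loss allowance and the cap stand in consecutive sentences and disagree. A Simon optimal design is chosen to meet its error limits with little to spare, so losing even one patient can breach one of them.
2. Under 8.1.2 a patient becomes evaluable only after at least one cycle and a re-evaluation, or on early progression. The attained number is therefore not fixed in advance. It may fall below 46, or reach as high as 50 if enrolment runs to the cap. With a boundary for 46 only, the cut-off for the primary conclusion could end up being chosen when the responses are already known, in a single-arm trial where one response can decide the result.

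**Working it through.** **Inputs (all from 12.3).** Null rate 0.40, target rate 0.60, alpha = beta = 0.10, first stage more than 7 of 18, final stage 22 of 46, loss 10%, cap 50. Sidedness is not stated; a Simon design is one-sided, and that is used here.

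**Formula.** With first-stage boundary r1 = 7, n1 = 18 and final rule of more than r responses among n evaluable,

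P(success | p) = Σ over x = 8 to 18 of P(X1 = x) × P(X2 > r − x), where X1 ~ Bin(18, p) and X2 ~ Bin(n − 18, p).

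Alpha is this at p = 0.40 and power is this at p = 0.60.

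**Step 1: reproduce the plan's design.** An exact search under the stated inputs returns 7/18 then 22/46 as the Simon optimal design, with success defined as more than 22. Alpha is 0.0952 and power 0.9004, so the design reproduces. The printed final boundary carries no sign of its own. Read as at least 22, alpha is 0.144 and power 0.922, which breaks the stated alpha. More than 22 is therefore taken as the intended rule.

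**Step 2: the allowance.**

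- 50 × 0.90 = 45, one below 46.
- 46 / 0.90 = 51.1, so 52 enrolled.
- The shortcut 46 × 1.10 = 50.6 also exceeds 50.
- (50 − 46) / 50 = 8%, the loss that the cap actually covers.

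**Step 3: the effect at 45 evaluable.**

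| Rule at n = 45 | Alpha | Power |
|---|---|---|
| more than 22 | 0.077 | 0.882 (beta 0.118) |
| more than 21 | 0.122 | 0.912 |

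With the 7/18 first stage, no cut-off at 45 meets both limits. Keeping 22 costs 0.900 − 0.882 = 0.018, or 1.8 points of power.

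**Step 4: how often the attained number differs from 46.** Assume that 50 are enrolled and that each is lost independently with probability 0.10. Losses are then Bin(50, 0.10):

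- 5 or more losses (n below 46): 0.569
- exactly 4 (n = 46): 0.181
- 3 or fewer (n above 46): 0.250

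**Step 5: a rule for any attained n.** Keep more than 7 of 18 and take the smallest final cut-off with exact alpha at most 0.10. The last column shows alpha if 22 were simply kept above 46.

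| Evaluable n | Success if more than | Alpha | Power | Alpha if 22 is kept |
|---|---|---|---|---|
| 39 | 19 | 0.093 | 0.872 | |
| 40 | 20 | 0.069 | 0.848 | |
| 41 | 20 | 0.087 | 0.876 | |
| 42 | 21 | 0.065 | 0.854 | |
| 43 | 21 | 0.082 | 0.879 | |
| 44 | 22 | 0.061 | 0.858 | |
| 45 | 22 | 0.077 | 0.882 | |
| 46 | 22 | 0.095 | 0.900 | 0.095 |
| 47 | 23 | 0.073 | 0.885 | 0.115 |
| 48 | 23 | 0.090 | 0.902 | 0.136 |
| 49 | 24 | 0.069 | 0.888 | 0.158 |
| 50 | 24 | 0.084 | 0.904 | 0.181 |

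Averaged over the attained n under the Step 4 model, this rule gives alpha 0.078 and power 0.881. The probability of 40 or fewer evaluable is 0.025.

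**The case against.** The best reply is about size. One patient and 1.8 power points look like a rounding shortfall; 10% is itself a planning guess; and at 45 with 22 kept, alpha falls to 0.077, so the error is conservative. All of that stands, which is why the lost power is the smaller half of the point.

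The alpha figures above 46 are conditional. They need enrolment near a cap that is a ceiling, fewer than 5 losses, and a decision to keep 22. The plan does not propose that decision, and the extreme at 50 needs no losses at all (0.9^50, about 0.005). This also stands, and those figures should be read only as the cost of one choice that the plan leaves open. Testing at exactly 46 evaluable would be a natural reading, but the plan does not say so, and at 10% loss the cap does not deliver 46.

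The greater-than sign before the first-stage boundary can be read across both stages. That is probably what was meant, and printing it settles the matter.

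Finally, the schedule is one convention among several. It does not restore power of 0.90 at every n, and its alphas are exact only if the first stage has exactly 18 evaluable patients. These are fair limits. The schedule does hold alpha at or below 0.10 without extra patients or a changed analysis set, and it removes discretion over the cut-off.

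**Conclusion.** The concern holds. At the plan's own 10% loss, 45 patients are evaluable where the design needs 46, and the stated alpha and beta cannot both be met there with the 7/18 first stage. The shortfall is small (power 0.882 against 0.900) and disappears with 4 losses or fewer. The design is not invalidated.

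The more consequential gap is that the primary success rule is defined for one evaluable number only. Under independent 10% loss from 50 enrolled, that number is attained with probability 0.18.

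The conclusion rests on three assumptions: a one-sided test, the final boundary read as more than 22, and, for the probabilities only, independent losses with enrolment to the cap. The 45-versus-46 arithmetic depends on none of them. Nothing in the documents suggests an intention to choose the cut-off late; the rule is simply not written down.

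**What to change.** Revise 12.3 as follows.

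1. Either restate the allowance as 8% (4 of 50), or keep 10% and state that power at 45 evaluable is about 0.88.
2. Print the final boundary for 46 evaluable as more than 22 responses.
3. State that, after more than 7 responses in 18 first-stage evaluable patients, the final cut-off is the smallest one with exact one-sided alpha at most 0.10 at the attained evaluable number: more than 20 at 41, 21 at 42 to 43, 22 at 44 to 46, 23 at 47 to 48 and 24 at 49 to 50. The same rule applies to smaller numbers, for example more than 20 at 40 and more than 19 at 39.

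The cost is a few lines of text and a slightly less favourable stated power or attrition figure. Enrolment and the evaluable set do not change.

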### 12.4 Safety Monitoring

Adverse events will be monitored on an ongoing basis by the central office and their frequencies reported bi-annually at investigators' meetings.

### 12.5 Interim Analysis

An interim assessment for safety of the first 5 patients treated within each cohort is planned. Results will be reviewed by the trial study team to determine if toxicity is acceptable to proceed.

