BRAF inhibitor therapy can have a radiosensitizing effect on cancerous and healthy tissue *[Zahnreich 2016]*. Radiation skin injury has been reported with concurrent use of BRAF inhibitors such as vemurafenib and dabrafenib and radiation including whole brain radiation for brain metastases. However, SRS limits dose to skin by using multiple beams from various angles, and only in a few fractions, we believe that this will not be a limiting toxicity. A recent study by Hecht et al. reported safety with SRS concurrent with a BRAF inhibitor such that no increase in skin toxicity or severe adverse events was observed *[Hecht 2015]*. No similar data exists for concurrent dabrafenib with trametinib. A recent report from the Eastern Cooperative Oncology Group (ECOG) acknowledged the lack of data with respect to SRS and concurrent BRAF inhibitors, and did not conclude any additional risk of radiation necrosis and hemorrhage from brain metastases when treated with a BRAF inhibitor and radiation. They suggested, based on limited literature and practice patterns, that the BRAF inhibitor be withheld 1 day prior to and after SRS, and 3 days prior to and after fractionated radiation; however, acknowledged that concurrent use should be evaluated on trial *[Anker 2016]*. Therefore, we will have an interim safety assessment after 5 patients in each cohort. If radiation dermatitis occurs, the study treatment will be modified so that dabrafenib and trametinib will be started two days after SRS is completed. These recommendations can be modified based on the physician's assessment of the risk of radiation skin injury.

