## 7.0 TREATMENT PLAN

Although the Canadian Cancer Trials Group acts as the coordinating agency for the trial, the responsibility for treatment of patients rests with the individual investigator.

In accordance with CCTG policy, protocol treatment is to begin within 2 working days of patient registration.

Patients should begin taking dabrafenib and trametinib a minimum of 7 days and a maximum of 14 days prior to commencement of SRS.

There will be 2 cohorts of patients. Each cohort is based on the number of brain metastases at presentation on T1-post gadolinium volumetric axial MRI.

Cohort 1: minimum 20 to 25 patients

Patients with 1-4 metastases will receive focal SRS to all lesions and dabrafenib + trametinib. Agents will begin a minimum of 7 days and a maximum of 14 days prior to SRS and continue post-SRS until progression or unacceptable toxicity.

Cohort 2: minimum 20 to 25 patients

Patients with 5-10 metastases will receive focal SRS to all lesions and dabrafenib + trametinib. Agents will begin a minimum of 7 days and a maximum of 14 days prior to SRS and continue post-SRS until progression or unacceptable toxicity.

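### The five-patient toxicity review states no criterion for unacceptable toxicity, and almost nothing at cohort level obliges a review of later patients

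*Combined protocol and SAP*

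**What the plan says.** Section 12.5 plans an interim safety look at the first five treated patients of each cohort and gives the decision in one sentence: "Results will be reviewed by the trial study team to determine if toxicity is acceptable to proceed". Section 12.2 sets the timing: "after 5 patients in each cohort have completed SRS with 4 weeks of follow-up time". Neither section names an event, grade, count or rate. Section 12.2 also explains why safety is evaluated by cohort: "However, toxicity may be different based on numbers of metastases treated".

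Beyond that look, Section 12.4 provides: "Adverse events will be monitored on an ongoing basis by the central office and their frequencies reported bi-annually at investigators' meetings". It attaches no threshold, no split by cohort and no consequence.

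One toxicity has a planned action, under the radiation therapy heading of Section 2.0: "If radiation dermatitis occurs, the study treatment will be modified so that dabrafenib and trametinib will be started two days after SRS is completed". It carries no grade and changes drug timing only. The next sentence makes it adjustable: "These recommendations can be modified based on the physician's assessment of the risk of radiation skin injury".

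Other safeguards work differently. The dose modifications in Section 7.1.3 act on individual patients. Sections 9.1 and 9.2 cover expedited reports of serious events, and Appendix III requires a treatment form every four weeks. Section 14.4 says who is told if the trial is discontinued. The only numerical stopping rule, the Simon design in Section 12.3, concerns response.

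**The concern.** Section 2.0 says that BRAF inhibitors can sensitise healthy tissue to radiation. After describing a reassuring report on SRS with a concurrent BRAF inhibitor, it adds: "No similar data exists for concurrent dabrafenib with trametinib". It also cites consensus advice to withhold the BRAF inhibitor around radiosurgery. Section 7.0 does otherwise: "Patients should begin taking dabrafenib and trametinib a minimum of 7 days and a maximum of 14 days prior to commencement of SRS", and Section 7.3.8 continues both drugs through the radiation days. Section 2.0 presents the interim safety look as the response to this uncertainty.

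The look is weakest when only one cohort is toxic, or when one event in five is judged tolerable; the protocol does not say whether it would be. After the look, pausing a cohort depends on someone noticing the counts and judging, without a reference number, that they are too high. At stake is the exposure of later patients in a toxic cohort. No efficacy inference is affected.

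**Working it through.** **Inputs from the documents.** Five patients per cohort at the look (12.5); SRS plus four weeks (12.2); drug lead-in of 7 to 14 days (7.0); 4 to 5 patients a month, maximum 50, accrual 12 to 18 months (12.3); at least 20 to 25 per cohort (7.0, 12.3), so a 20/30 split is possible; symptomatic necrosis below 10% after SRS (3.4).

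**Assumed, because the documents give no value.** True toxicity rates of 10% to 40%; a 10% reference rate; an even split of accrual; onset times.

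**The plan's own figure.** There is none for toxicity. The efficacy rule (7/18, then 22/46, success if more than 22) reproduces: the sum over x = 8 to 18 of b(x; 18, p) × P(Bin(28, p) ≥ 23 − x) is 0.095 at p = 0.40 and 0.900 at p = 0.60.

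**What five patients can show, one cohort.**
- No event, (1 − p)^5: 0.8^5 = 0.33 at 20%; 0.7^5 = 0.17 at 30%.
- At most one event, (1 − p)^5 + 5p(1 − p)^4: 0.74 at 20%; 0.53 at 30%. This matters only if one in five is accepted.
- With 0/5, the one-sided 95% upper limit is 1 − 0.05^(1/5) = 0.45.
- If both cohorts share the rate, at least one event in ten: 1 − 0.8^10 = 0.89; 1 − 0.7^10 = 0.97.

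**Patients beyond the look.** At most 50 − 10 = 40. If registration continues meanwhile, about 10 + 4 × (7 + 28)/30.4 = 14.6 to 10 + 5 × (14 + 28)/30.4 = 16.9 are registered by the review, leaving 33 to 35.

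**Example boundary.** For each n, take the smallest k ≥ 2 with P(X ≥ k | n, 0.10) ≤ 0.052. This gives 2 events in 2–3 patients, 3 in 4–8, 4 in 9–14, 5 in 15–20, 6 in 21–27 and 7 in 28–30. Exact patient-by-patient recursion gives the first two rows below.

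| Probability of firing at true rate | 10% | 15% | 20% | 30% | 40% |
|---|---|---|---|---|---|
| 25 patients, immediate outcomes | 0.10 | 0.28 | 0.51 | 0.86 | 0.98 |
| 30 patients, immediate outcomes | 0.11 | 0.31 | 0.57 | 0.91 | 0.99 |
| During accrual of 25, prompt reports | 0.04–0.06 | 0.15–0.20 | 0.32–0.41 | 0.71–0.79 | 0.92–0.96 |
| During accrual of 25, form lag | – | – | 0.25–0.33 | 0.62–0.73 | 0.87–0.93 |

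The accrual rows are simulated: Poisson registration at 2 to 2.5 a month per cohort, SRS ten days after registration, onset within one month of SRS, firing before the 25th registration, and n counting registered patients. The form lag is uniform over 0 to 6 weeks (a four-week cycle plus the two weeks allowed in Appendix III). Counting only patients who have started SRS, as the fix does, raises the prompt-report figures slightly: a repeat with 8,000 runs per setting gave 0.05–0.07, 0.36–0.42 and 0.72–0.80 at 10%, 20% and 30%.

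At five patients the boundary is 3 events. Applied only there, it fires with probability 0.16 at a 30% rate, so the count has to continue past the fifth patient.

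**Late necrosis.** With onset assumed uniform over 3 to 12 months and prompt reports, firing during accrual at a 30% rate has probability 0.021–0.075, or about 0.25 at 1.4 a month (25 patients in 18 months).

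**False pauses.** At 10%, 0.097 per cohort and 1 − 0.903² = 0.185 for either. At 15%, 0.277 and 1 − 0.723² = 0.477.

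**The case against.** Judgement-based review of a small phase 2 trial is a legitimate choice. The drugs are commercially available, SRS is standard, there is no dose escalation, and Section 7.1.3 gives individual hold and stop rules. Section 2.0 also reports no excess of skin toxicity or severe events with SRS and a concurrent BRAF inhibitor, and a cooperative-group report that found no added risk of necrosis or haemorrhage. This lowers the urgency, but it does not supply data on the triple combination.

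Four stronger readings are tempting, and the documents do not support them.
- A reader might infer that toxicity is not monitored after ten patients. Section 12.4 plans ongoing monitoring and, over 12 to 18 months, two or three frequency reports. Serious event reports, four-weekly forms and discontinuation all leave room for ad hoc action. What is missing is a number that obliges it.
- A reader might infer that accrual runs on during the review. Section 12.5 can equally be read as a gate, so only the limit of 40 is safe.
- A reader might infer that SRS injury escapes expedited reporting. Section 9.1 covers events related to protocol treatment, which includes radiation, although it then defines relatedness by the protocol agent. It also has a judgement clause. A gap is possible, not established.
- A reader might infer that each cohort is judged on five patients alone. Section 12.2 describes the look for both cohorts, so the team may see ten together, which is far more informative if the rates are shared.

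The objection that any boundary is arbitrary without a clinically agreed rate stands. The 10% figure is borrowed from the necrosis ceiling in Section 3.4 and is not the rate of the proposed composite.

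**Conclusion.** The point holds in limited form. The one toxicity review tied to a decision has no stated criterion. After it, only an ungraded, adjustable dermatitis instruction acts at cohort level. A cohort with a true rate of 20% to 30% passes its five-patient look without an event with probability 0.33 to 0.17. These binomial figures are exact for the assumed rates. The performance of the example boundary also depends on the reference rate, onset times and accrual split, none of which the documents settle. It offers useful protection against early toxicity and little against necrosis arising months after SRS. The primary endpoint, its error rates and the sample size are unaffected. This is a recommendation at the lower end of what should be changed.

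**What to change.** 1. In Sections 12.4 and 12.5, have the central office keep a running count, by cohort, of grade 3 or higher SRS-related CNS toxicity (including symptomatic necrosis) or in-field skin toxicity among patients who have started SRS. Pause registration to that cohort for study-team review at a pre-specified boundary. Example at a 10% reference rate, which the team must confirm or replace before use: 2 events in 2–3 patients, 3 in 4–8, 4 in 9–14, 5 in 15–20, 6 in 21–27, 7 in 28–30. If 15% is the acceptable background, use 2 in 2, 3 in 3–5, 4 in 6–9, 5 in 10–13, 6 in 14–18, 7 in 19–23, 8 in 24–27, 9 in 28–30 (same construction, tail at most 0.0465). With 25 patients that fires with probability 0.10, 0.25, 0.65 and 0.91 at 15%, 20%, 30% and 40%. The team stays free to act on fewer events.
2. Add these events to the list in Section 9.1, which already names protocol-specific events such as retinal vein occlusion, so that they arrive within 24 hours whether attributed to drug or SRS.
3. State in Section 12.4 that the rule guards against early toxicity and will seldom pause accrual in time for late necrosis.

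The cost is one paragraph, a small table, one bullet and a few extra 24-hour reports, with no new committee or visits. The downside is an unnecessary short pause: about 0.10 per cohort at a true 10% rate with the 10% boundary, rising to 0.28 if the background is 15%.
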